#### **1.2 Sample size**

There is no previous study to reference, the researchers have opted for a pilot study with a sample size of 28 participants.

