## **2. Research Format**

Pilot study and one group before-after design.

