#### **3) Skin Condition Measurement for Volunteers**

Volunteers receive appointments for skin condition measurements. Skin measurements occur at the same time each week. Rescheduling is allowed for volunteers unable to make appointments due to non-study-related commitments or COVID-19 concerns.

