Positions are determined based on Hamilton's classification of contour changes of facial skin, specifically targeting static wrinkles effectively. Volunteers will calculate the average value for both areas to represent their data. The assessment will be performed by two board-certified dermatologists, each evaluating both areas, ensuring a thorough and reliable evaluation of wrinkle improvement.

The positions for measurements using Visioscan

Visia-CR is utilized as a detailed facial imaging system to compare changes before and after product usage. The assessment is done by comparing images using the Subject Global Aesthetic Improvement Scale (SGAIS) as follows:

Score 1: Worse (no improvement)

Score 2: Mild improvement (<25% improvement)

Score 3: Improvement (25-49% improvement)

Score 4: Much improved (50-74% improvement)

Score 5: Very much improved (75% improvement or more)

The evaluation is conducted by two board-certified dermatologists, each specializing in skin health. The images captured by Visia-CR allow for a thorough comparison of facial conditions before and after product usage, providing a detailed understanding of the product's impact on the skin's aesthetic improvement.

The medical technicians will perform measurements of skin moisture, water loss, skin elasticity, skin color, and capture facial images using a specialized imaging device, taking approximately 30 minutes for each

participant. This research will measure these parameters on the first day (d1) before applying EGF serum to establish a baseline.

7) Baseline Measurements:

Participants will undergo measurements on the first day, assessing moisture, water loss, skin elasticity, skin color, and facial images using Corneometer, Tewameter, Cutometer, and imaging devices.

8) Application of EGF Serum:

Participants will apply EGF serum twice daily for 8 weeks, using three drops each time, covering the entire face.

9) Sunscreen Application:

After using EGF serum in the morning, participants will apply Skin Intelligence Sunscreen Cream SPF30 PA+++, using 2 fingertip units (approx. 1 gram) each time.

10) Second Visit (2 Months):

Participants return for a second assessment after 2 months, with measurements conducted similar to the baseline.

11) Subsequent Visits:

Participants stop using the serum and return for measurements in the 3rd and 4th months, following the same procedure.

Note:

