## 7. Statistical Analysis

7.1 Descriptive Statistics for General Participant Information: Descriptive statistics will be used for continuous quantitative data, presenting mean and standard deviation or median and interquartile range (IQR). For non-continuous quantitative data and qualitative data (ordinal scale, nominal scale), results will be reported as percentages.

7.2 Primary Outcome Analysis: The primary outcome data, comparing values for skin moisturization, water loss from the skin, skin elasticity, skin color measurement, and wrinkle assessment before and after using the serum at 8 weeks, 12 weeks, and 16 weeks, will be analyzed. If the data follow a normal distribution, a repeated-measure ANOVA will be used, with  $p < 0.05$  considered statistically significant. In cases where the data distribution is not normal, the Wilcoxon signed-rank test will be employed.

7.3 Descriptive Statistics for Adverse Events: Descriptive statistics, reported as percentages, will be used to analyze adverse events after using the serum with Epidermal Growth Factor.

7.4 Descriptive Statistics for Participant Satisfaction: Descriptive statistics, reported as percentages, will be used to analyze participant satisfaction after using the serum with Epidermal Growth Factor.

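### Section 7.2 sets no missing-data rule, and a classical repeated-measures ANOVA would by default discard the observed week 8 readings of anyone who misses week 12 or 16

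*Combined protocol and SAP*

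**What the plan says.** The study has a single group (Section 2: "Pilot study and one group before-after design"). On size, Section 1.2 states that "the researchers have opted for a pilot study with a sample size of 28 participants".

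Section 7.2 covers moisture, water loss, elasticity, skin colour and wrinkles "before and after using the serum at 8 weeks, 12 weeks, and 16 weeks, will be analyzed". For normally distributed data: "If the data follow a normal distribution, a repeated-measure ANOVA will be used". Otherwise: "In cases where the data distribution is not normal, the Wilcoxon signed-rank test will be employed".

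The activity table in Section 4 places the instrument readings at d1 and weeks 8, 12 and 16. Serum is used for 8 weeks. Section 2.1, item 11 then says: "Participants stop using the serum and return for measurements in the 3rd and 4th months, following the same procedure". Week 8 is therefore the only measured visit at the end of serum use, and the other two post-baseline visits are off serum.

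On attendance, Section 2.1, item 3 says: "Rescheduling is allowed for volunteers unable to make appointments due to non-study-related commitments or COVID-19 concerns". Section 5 lets participants withdraw at any time. No section gives an analysis set, a missing-data rule, an estimation method, an expected dropout rate, or a primary visit or contrast.

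**The concern.** A classical repeated-measures ANOVA works on complete rows. With four visits in the row, whether a person's week 8 value counts depends on whether that person comes back 4 and 8 weeks later, after the serum has been stopped. Three things are at stake.

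- **Precision.** Week 8 readings already collected from a group of 28 would be set aside.
- **Bias.** If return for the later visits is related to how the skin responded by week 8, the completers' mean week 8 change no longer estimates the change in everyone measured at week 8. There is no control group to reveal the shift.
- **Consistency between measures.** The signed-rank test, if applied to d1 and week 8 pairs, keeps a person whom the ANOVA drops. The normality result for each measure could then decide who is analysed, so that week 8 results in one study rest on different participants.

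**Working it through.** **Inputs.** From the documents: n = 28, readings at d1 and weeks 8, 12 and 16, and significance at p < 0.05 (sidedness not stated; two-sided assumed here). The documents give no effect size, SD, power or dropout rate, so the figure of 28 has no calculation to reproduce. All attendance rates below are assumptions.

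**1. Does the method drop people?** Data were simulated for 28 participants, 4 of them without week 16. A standard repeated-measures ANOVA routine rejected the data as unbalanced. It ran only on the 24 completers, discarding four observed week 8 values. A linear mixed model used all 28 × 4 − 4 = 108 readings.

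**2. Precision.** Let each post-baseline visit be missed independently with probability q. The expected number with a week 8 reading is 28(1−q). The expected number with all visits is 28(1−q)³. The fair comparison is between these two, because a person who misses week 8 has no week 8 reading to lose. The SE ratio is √[(1−q)/(1−q)³] = 1/(1−q).

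| q | With week 8 | All visits | SE ratio |
|---|---|---|---|
| 5% | 26.6 | 24.0 | 1.05 |
| 10% | 25.2 | 20.4 | 1.11 |
| 15% | 23.8 | 17.2 | 1.18 |

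If all 28 attend week 8 and k of them are dropped later, the ratio is √[28/(28−k)]: 1.018 for k = 1, 1.038 for k = 2, 1.080 for k = 4 and 1.183 for k = 8. The 95% interval half-width, in SDs of the change, is t(0.975, n−1)/√n: 0.388 at n = 28, 0.404 at 26, 0.422 at 24 and 0.468 at 20.

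**3. Bias when the measured change itself drives attendance.** Let the third with the poorest week 8 change be lost with probability a, and the rest with probability b. For a normal change the lowest-third cut is at −0.431 SD, where the normal density is 0.3636. The bias of the completers' mean, in SDs of the change, is 0.3636(a − b)/(1 − a/3 − 2b/3).

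- a = 0.30, b = 0.05: 0.3636 × 0.25/0.867 = 0.105
- a = 0.40, b = 0.05: 0.3636 × 0.35/0.833 = 0.153
- a = 0.50, b = 0.10: 0.3636 × 0.40/0.767 = 0.190

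The overall losses are 13%, 17% and 23%. Simulation of 40,000 trials per scenario agrees with these biases.

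**4. Direction.** A second simulation (20,000 trials of 28) used a logistic dependence of attendance on the week 8 change, slope 1 per SD. With 10%, 20% and 30% lost, the bias was:

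- +0.09, +0.17 and +0.25 SD when poor responders stay away
- −0.09, −0.17 and −0.25 SD when good responders stay away
- within 0.002 SD of zero when loss is unrelated to response

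The mean of all observed week 8 changes was within 0.003 SD of the truth in every case.

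**5. Weaker coupling.** If attendance follows perceived benefit, and perception correlates r with the instrument reading, the bias in step 3 is multiplied by r. For r = 0.5 it is about 0.05, 0.08 and 0.09 SD. For r = 0.3 it is about 0.03, 0.05 and 0.06 SD.

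**The case against.** The plan does not say that only complete cases are analysed. That is inferred from the classical form of the named method, and a repeated-measures analysis fitted as a mixed model would keep everyone. This is correct, and it limits the point to what happens by default. But Section 7.2 names neither a mixed model nor any rule for missing visits, so the default would apply. If a mixed model was intended, saying so is the same edit. How the signed-rank test would be applied across four visits is also unstated, so the mismatch between measures is a possibility and not a stated feature.

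Rescheduling should recover many missed appointments, and people who miss week 12 may well be the same people who miss week 16. Both reduce the loss below the independent-visit figures. Neither removes it, because rescheduling does not cover withdrawal.

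A reader might infer that the plan will overstate the on-serum effect, or that its week 8 test has a false-positive rate of 8-15%. The documents support neither. The 8-15% comes from the three scenarios in step 3, where the measured change itself decides who returns. With a correlation of 0.5 between perception and reading, simulation gives about 6-8%, and with 0.3 about 5-6%. Section 7.2 also names no week 8 test as primary. The documents give no attrition rates or reasons, and the sign reverses if satisfied participants are the ones who stay away.

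A reader might also take 24, 20 or 17 of 28 as the loss caused by the ANOVA. Those counts include people missing week 8 itself, so the SE ratios in step 2 are the proper measure.

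**Conclusion.** The point holds as a default consequence of an unstated rule. As worded, Section 7.2 leads a classical repeated-measures ANOVA to discard observed week 8 readings when a later off-serum visit is missed. Under assumed independent missingness of 5%, 10% or 15% per visit, the week 8 standard error rises about 5%, 11% or 18%. It rises about 2-4% if only one or two people are lost, and less than the independent-visit figures if missed visits cluster or are rescheduled. Bias in the completers' week 8 change is possible but not established. Its direction and size depend on why people stay away, and 0.10-0.19 SD is an upper scenario for overall losses of 13-23%. For a pilot of 28 this is a modest weakness that costs almost nothing to remove: a cheap improvement.

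**What to change.** In Section 7.2, for moisture, water loss, elasticity and melanin index, replace the repeated-measures ANOVA by a linear mixed model:

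- Fit visit (d1, weeks 8, 12 and 16) as a categorical fixed effect, using every available reading from all enrolled participants.
- State the small-sample choices in advance, for example unstructured within-participant covariance fitted by REML with Kenward-Roger degrees of freedom, and a random participant intercept if that does not converge.
- Report week 8, 12 and 16 minus d1, with the number of participants behind each contrast.
- For a clearly skewed measure, fit the same model to log readings, so that all four measures use the same approach to missing visits.
- State that the wrinkle improvement grade, which the dermatologists rate only at weeks 8, 12 and 16, is outside this model and is summarised at each visit from all observed ratings.

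The cost is wording only: no new data, visits or participants, and standard software. The small downside is that the model assumes missingness depends only on observed readings, and the covariance fallback must be fixed beforehand because n is 28. The change does not make up for the lack of a control group.

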## 6) Evaluation Parameters

Five parameters will be measured using various tools to assess experiment results.

Measurement of skin moisture and water loss using Corneometer and Tewameter, respectively.

Measurement of skin elasticity using Cutometer.

Measurement of skin color using Mexameter.

Evaluation of skin wrinkles using Visioscan.

[figure not shown]
Assessment of facial skin changes using Visia-CR imaging.

These steps are meticulously designed to ensure high-quality and reliable data for the dermatological research.

The measurements for Corneometer, Tewameter, and Cutometer will be taken at four specific positions:

- Right Malar prominence area
- Left Malar prominence area
- Central forehead
- Central chin

Measurements will be performed three times at each position, as illustrated in the diagram below. Each volunteer will calculate the average value for all four areas to represent their data. Assessors will use a marking technique on transparent sheets to ensure consistent measurement points are maintained across all sessions.

[figure not shown]

The positions for measurements using Corneometer, Tewameter, and Cutometer

When using the Mexameter to measure the Melanin Index (MI), readings will be taken at two specific positions:

- Right Malar prominence area
- Left Malar prominence area

Measurements will be conducted three times at each position, as depicted in the diagram below. Each volunteer will calculate the average value for both areas to represent their data. Assessors will utilize a marking technique on transparent sheets to ensure consistent measurement points across all sessions.

The positions for measurements using Mexameter

Visioscan is used to assess wrinkles using a 4-grade percentage wrinkle improvement scale as follows:

Grade 1 (0-25%): No change to a slight improvement in wrinkles.

Grade 2 (> 25-50%): Moderate improvement in wrinkles.

[figure not shown]
Grade 3 (50-75%): Marked improvement in wrinkles.

Grade 4 (>75%): Significant to no wrinkles.

The assessment involves scoring at four positions:

- Right crow feet area
- Left crow feet area
- Right cheek line area
- Left cheek line area

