**4. Table of activities:**

Activities	Day/wk	d1	2 wk	4 wk	8 wk	12 wk	16 wk
Record data		✓					
Apply EGF serum		✓	✓	✓	✓		
Apply sunscreen cream		✓	✓	✓	✓	✓	✓
Measuring skin moisture and water loss using Tewameter and Corneometer		✓			✓	✓	✓
Measuring skin elasticity using Cutometer		✓			✓	✓	✓
Measuring melanin index using Mexameter		✓			✓	✓	✓
Measuring wrinkle using Visioscan		✓			✓	✓	✓
Capturing facial images using Visia-CR		✓			✓	✓	✓
Evaluation by Specialists (Two Board-Certified Dermatologists)					✓	✓	✓
Assessment of Participant Satisfaction					✓	✓	✓
Assessment of adverse effects					✓	✓	✓

Assessment of adverse effects via videocall application line		✓	✓			
--	--	---	---	--	--	--

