**Research Outcomes:**

6.1 Primary Outcome: Measurement of five parameters, including skin moisturization, skin elasticity, skin color, skin wrinkle assessment, and facial imaging using the Visia-CR system. Measurements will be taken at baseline, 2 months, 3 months, and 4 months.

6.2 Secondary Outcomes:

1) Assessment of participant satisfaction post-treatment at 2, 3, and 4 months using a quartile grading system (0 = unsatisfied, 1 = slightly satisfied, 2 = satisfied, 3 = very satisfied).

2) Evaluation of adverse events, including irritation, rash occurrence, new dark spots, and infections post-treatment through videocall applications at 2 weeks and 4 weeks. On-site evaluations will occur at 2 months (after completion), 3 months, and 4 months.

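### Section 7.2 lets an unspecified normality check choose between a four-visit ANOVA and a two-visit Wilcoxon test, without naming the contrast or the primary time point

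*Combined protocol and SAP*

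**What the plan says.** Section 7.2 (Primary Outcome Analysis) compares the primary measures "before and after using the serum at 8 weeks, 12 weeks, and 16 weeks". It then gives two tests: "If the data follow a normal distribution, a repeated-measure ANOVA will be used", with significance at p < 0.05; otherwise, "In cases where the data distribution is not normal, the Wilcoxon signed-rank test will be employed".

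Section 6.1 lists the same visits in months and ranks none above the others: "Measurements will be taken at baseline, 2 months, 3 months, and 4 months". Section 2.1 fixes where treatment falls among them. Item 8 says "Participants will apply EGF serum twice daily for 8 weeks", and item 11 says "Participants stop using the serum and return for measurements in the 3rd and 4th months". Week 8 is therefore the end of the serum period, and weeks 12 and 16 are off serum.

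Neither Section 6.1 nor Section 7.2, nor any other section, names a primary time point, a follow-up contrast after the ANOVA, the pair of visits for the Wilcoxon test, or an adjustment across visits. Nor does any say how normality is judged, or on which values (raw values, changes or residuals; per parameter or per visit).

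**The concern.** The two tests are not counterparts. Over four visits, a repeated-measures ANOVA by default asks whether any visit mean differs from any other. A Wilcoxon signed-rank test asks whether one visit differs from one other. The rank counterpart of the four-visit test is Friedman's.

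The difference matters because serum stops between the second and third measurements. A significant omnibus ANOVA does not by itself show a change at the end of the 8-week serum period, since the signal may come from an off-serum visit. A non-significant one can hide a week-8 change that fades afterwards, and if contrasts are examined only after a significant ANOVA, that change would never be tested. If the check is applied parameter by parameter, which is the natural reading though not stated, hydration could be judged on one question and melanin index on another, both reported as p < 0.05.

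**Working it through.** The plan has no figure to reproduce: 28 is a pilot choice with no power calculation. The steps below show what each reading of Section 7.2 implies.

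**1. Count the tests per parameter.** With four visits and 28 participants, the omnibus ANOVA is one F test on 3 and 3 × 27 = 81 degrees of freedom. Wilcoxon tests of each later visit against baseline would be three tests.

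**2. Set an illustrative effect.** Assume a week-8 change of 0.55 SD of the paired difference. The noncentrality is 0.55 × √28 = 2.91 and the two-sided critical value on 27 df is 2.052, so the paired t test has 80.1% power. The 95% CI half-width is 2.052/√28 = 0.39 SD.

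**3. Simulate.** Only n = 28 comes from the documents. Assumed: complete normal data; between-visit correlation 0.6–0.8, either equal or AR(1); and three profiles in SD of the week-8 paired difference: fading (0.55, 0.275, 0.1375), sustained (0.55 throughout), and week 8 only (0.55, 0, 0). GG is the Greenhouse-Geisser correction.

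Share of data sets in which two analyses of the same data give different verdicts at 0.05, with an effect present:

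| Comparison | Equal correlations | AR(1) |
|---|---|---|
| Omnibus ANOVA v week-8 Wilcoxon, uncorrected | 15–16% | 22–33% |
| The same, with GG | 16–17% | 25–41% |
| Contrasts gated by the omnibus ANOVA v Wilcoxon | 8–15% | 21–39% |
| GG ANOVA v Friedman | 15.6–20.2% (both structures) | |
| Week-8 paired t v week-8 Wilcoxon | 4.5–5.1% (both structures) | |

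The last row is what remains if the ANOVA branch reports ungated baseline contrasts.

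**4. Power.** The week-8 paired t test has 79.8–80.6% throughout. The uncorrected ANOVA has:

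| Profile | Equal correlations | AR(1) |
|---|---|---|
| Fading | 69.6–70.2% | 52.5–57.4% |
| Sustained | 84.0–84.5% | 61.4–67.7% |
| Week 8 only | 83.9–84.7% | 68.7–73.4% |

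The ANOVA is not uniformly worse. It gains a little under equal correlations for sustained or week-8-only effects and loses elsewhere.

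**5. A change only after stopping.** If only week 16 differs (0.5 SD paired change, equal correlation 0.6), the ANOVA is significant in 76% of data sets and the week-8 contrast in 5%.

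**6. No change.** The ANOVA rejects in 5–7% (4–5% with GG). At least one of three unadjusted Wilcoxon tests rejects in 11–12%; independent tests would give 1 − 0.95³ = 14.3%.

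**The case against.** The strongest reply is that Section 7.2 opens with before-after comparisons at three visits, in a one-group before-after design. The natural meaning is baseline against each visit, and that sentence may govern both branches. If so, both tests answer the same three questions and the week-8 disagreement is only about 5%. This stands as a possible reading. What it does not settle is whether the contrasts are reported regardless of the omnibus result, which pairs Wilcoxon covers, or how the three are adjusted. Two analysts could follow the text and report different results.

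A reader might infer that the choice of branch reverses 15–41% of the plan's conclusions. The documents do not support that, for three reasons:
- The range applies only if the ANOVA is read as omnibus. Gated contrasts give 8–39%.
- Under equal correlations it is no larger than ANOVA v Friedman, so there it is no evidence that the mismatch of questions adds to what a matched rank test would do. A clear excess appears only under AR(1), which is assumed.
- It ignores how often the check switches tests. If a Shapiro-Wilk test at 0.05 were applied at each of the four visits, it would fire in 16–20% of normal data sets, and fire together with a changed verdict in 2.4–7.1%. Non-normal data, where the rule is meant to act, were not simulated.

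A reader might also infer a false-positive rate of 11–12%. That needs a rule that any one significant visit counts as success, and the plan states none.

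**Conclusion.** The concern holds as a gap in specification with a mismatched pair of tests. Section 7.2 does not say whether the ANOVA branch delivers an omnibus test, gated contrasts or ungated baseline contrasts, and its non-normal alternative compares a pair of visits it does not name. Under the first two readings, p < 0.05 can mean different things for different parameters; under the third, the branches largely agree.

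The percentages rest on assumed effects, correlations and normal complete data. They illustrate the readings and are not error rates of this plan. Severity is low: this is an uncontrolled pilot of 28 people with no stated power or decision rule, and the point concerns how a before-after change is read, not whether the serum caused it.

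Two neighbouring matters are separate. Multiplicity across parameters is one. The other is which wrinkle variable Section 7.2 means: the evaluation section describes an improvement grade ("Visioscan is used to assess wrinkles using a 4-grade percentage wrinkle improvement scale as follows"), while the activities table also schedules "Measuring wrinkle using Visioscan" on day 1.

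**What to change.** For hydration, water loss, elasticity and melanin index, replace the data-driven switch with one prespecified contrast, reported for every parameter whatever its distribution:

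- **Primary:** week 8 minus baseline, with a 95% CI and paired t test, because week 8 ends the serum period. If visits are missing, take the same contrast from a repeated-measures model. If persistence matters as much to the sponsor, another single time point may be named instead.
- **Secondary:** weeks 12 and 16 minus baseline, Holm-adjusted across the two or labelled exploratory.
- **Sensitivity:** Wilcoxon signed-rank test on the primary difference, always reported.

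A minimum alternative keeps both tests but states the follow-up contrasts and whether they are gated, the Wilcoxon pairs, the adjustment, and how and on which values normality is checked.

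The cost is SAP wording only, with no new data or participants. Power is slightly below the ANOVA's (about 80% v 84–85%) if correlations are equal and the effect is sustained or confined to week 8. Holm across weeks 12 and 16 lowers week-12 power from 80% to 76% in the sustained, equal-correlation case. In return, the chance that either is falsely significant falls from 8–9% to 4–5%.
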